6.4. Pre-Screening/Screening/Run-in/Randomization Failures

A participant will be assigned a participant number at the time the informed consent is signed at Visit 0.

The study site will be responsible for reporting pre-screen failures. The following information will be collected in the eCRF for participants who are pre-screen failures:

- Demographic information including race, age and gender
- Participant number
- Serious Adverse Event information only for any SAE considered as related to study participation
- Investigator signature page

For the purposes of this study, pre-screening failures, screening failures, run-in failures and randomization failures will be defined as follows:

- **Pre-screening failures:** those participants that sign the informed consent document but do not have a Visit 1 (Screening) procedure.

- **Screening failures:** those participants that complete at least one Visit 1 (Screening) procedure but do not enter the run-in period.
A participant who completes Visit 1 assessments and is dispensed the study medication for the run-in period is considered to have entered the run-in period.
- **Run-in failures:** those participants that enter the run-in period but do not have any Visit 2 (Randomization) procedures.
- **Randomization failures:** those participants that complete at least one Visit 2 (Randomization) procedure but do not enter the double-blind study treatment period.
Any participant who completes the run-in period and then meets the randomization criteria and is dispensed the double-blind study treatment at Visit 2 is considered to have entered the treatment period.

RAMOS NG will be contacted to register the participant.

In order to ensure transparent reporting of screen/run-in failure participants, meet the Consolidated Standards of Reporting Trials (CONSORT) publishing requirements, and respond to queries from Regulatory authorities, a minimal set of screen/run-in/randomization failure information is required including demography, screen/run-in/randomization failure details, eligibility criteria, and any SAEs (see Section 9.2.4 and Appendix 4). Further details are provided in the study-specific eCRF completion guidelines document.

Re-screening of subjects will be permitted; however, advance written approval to proceed with re-screening a subject must be obtained from the Medical Monitor (for contact details, see the medical monitor/Sponsor Information Page at the beginning of this protocol).

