7.7. Treatment Compliance

When participants are dosed at the site, they will receive FF 100 mcg and study treatment under medical supervision. The date and time of each dose administered in the clinic will be recorded in the eCRF. The dose of study treatment and study participant identification will be confirmed at the time of dosing by a member of the study site staff.

When participants self-administer study treatment(s) at home, compliance with study treatment will be assessed through querying the participant during the site visits and recording the number of doses remaining in the ELLIPTA in the eCRF (see the SRM for details). A record of the number of ELLIPTAs dispensed to each participant must be maintained and reconciled with study treatment and compliance records.

Participant compliance with FF 100 mcg and study treatment will be assessed at scheduled clinic visits by reviewing the eDiary and information from the dose counter on the returned inhaler(s) (see Section 7.1.3). Participants should be $\geq 80\%$ to $\leq 120\%$ compliant on taking both FF 100 mcg and study treatment between each pair of

compliant on taking both FF 100 mcg and study treatment between each pair of scheduled and consecutive on-treatment clinic visits, as applicable. Participants who fall outside this range should be re-educated on treatment compliance by their site. This re-education should be documented in the participant's source document. If FF 100 mcg and/or study treatment is prematurely discontinued during the course of the study or compliance repeatedly falls outside of acceptable ranges, the study sponsor/site monitor must be contacted to discuss participant eligibility for continued participation in the study.

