10.5. Data Analysis

10.5.1. Analysis population

The following participant populations will be identified:

All Participants Enrolled Population: This population will comprise all participants for whom a record exists on the study database, including pre-screened participants that sign the informed consent document but do not complete a Visit 1 (screening) procedure (i.e., pre-screening failures), or participants that complete at least one Visit 1 procedure but do not enter the run-in period (i.e., screening failures). This population will be used for the summary of participant disposition.

All Participants Screened Population: This population contains all participants that complete at least one Visit 1 (Screening) procedure. This population will be used for the summary of participant disposition (including reasons for screening failures and run-in failures) and for the listing of AEs and SAEs for non-randomized participants.

ITT Population: This population will comprise all randomized participants, excluding those who were randomized in error. A participant who is recorded as a screen failure or

run-in failure, but is randomized and does not receive a dose of study treatment, is considered to be randomized in error. Any other participant who receives a randomization number will be considered to have been randomized. This will constitute the primary population for all efficacy and safety analyses.

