10.6. Statistical Analysis

Where possible, data from participants who withdraw prematurely from the study treatment or the study will be included in any relevant analyses. Specific details for inclusion will be detailed in the RAP.

In general, the baseline value is the last assessment value prior to randomization at Visit 2 for the efficacy endpoints based on assessments at clinic visits. The covariates to be considered in the efficacy analyses include age, sex, and the baseline value, if relevant. Other covariates, if appropriate, may be considered. Specific details will be provided in the RAP.

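### Section 10.5.1 bases the safety analyses on ITT, which does not require a dose, so randomized but never-dosed participants can enter the safety denominators

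*Protocol*

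**What the plan says.** Protocol Section 10.5.1 names three populations: All Participants Enrolled, All Participants Screened, and ITT. None is defined by having taken a dose of double-blind treatment.

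On ITT it says: "This population will comprise all randomized participants, excluding those who were randomized in error". That exclusion applies to two kinds of recorded failure, at screening and in run-in, under one condition. For the second kind the text reads: "run-in failure, but is randomized and does not receive a dose of study treatment, is considered to be randomized in error". Everyone else is kept: "Any other participant who receives a randomization number will be considered to have been randomized". The paragraph ends by assigning ITT to safety as well as efficacy: "This will constitute the primary population for all efficacy and safety analyses".

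Section 6.4 has a further category, randomization failures, defined as "those participants that complete at least one Visit 2 (Randomization) procedure but do not enter the double-blind study treatment period". The exclusion in 10.5.1 does not mention this category.

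**The concern.** An adverse event proportion is meant to describe people exposed to the treatment. A participant who never took a dose adds one to the denominator and cannot have an event caused by the drug, so including such participants lowers the reported proportion. In a comparison with placebo this shrinks absolute differences when non-dosing is balanced, which is the wrong direction in which to err on safety.

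The exclusion rule also fits poorly with Section 6.4. That section defines run-in failures as having no Visit 2 procedure and screening failures as never entering run-in. Randomization is itself a Visit 2 activity in the Schedule of Activities. Someone randomized at Visit 2 who then does not start treatment therefore matches neither of the two categories that 10.5.1 removes.

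Comparing safety and tolerability with placebo is a stated objective (Section 4), so the population for those summaries should be one that supports it.

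**Working it through.** **Who stays in, reading 10.5.1 against 6.4**

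| Randomized, never dosed, and… | Section 6.4 status | In ITT under 10.5.1? |
|---|---|---|
| recorded as a screen or run-in failure | screening or run-in failure | No, randomized in error |
| given a number at Visit 2, did not enter treatment | randomization failure | Yes |
| dispensed treatment at Visit 2, took none | counts as having entered treatment | Yes |

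A participant who fails the Visit 2 criteria and receives no randomization number is not in ITT. Only the second and third rows matter.

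**Inputs**
- Arm size: 128 randomized (Section 10.2). This figure reproduces: 115 / (1 − 0.10) = 127.8, rounded up to 128.
- Never-dosed per arm, k: not given in the documents. Assumed range 0 to 6.
- True adverse event proportion among the dosed, p: assumed 10% for illustration.
- Events among the never-dosed: assumed none. For a given k this gives the largest dilution, provided the never-dosed rate is no higher than p. If they report background events, the understatement is smaller.

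**Formulas**
- Reported proportion = p × (128 − k) / 128
- Relative understatement = k / 128

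| k | Reported when true value is 10% | Relative understatement |
|---|---|---|
| 0 | 10 × 128/128 = 10.0% | 0% |
| 1 | 10 × 127/128 = 9.9% | 1/128 = 0.8% |
| 3 | 10 × 125/128 = 9.8% | 3/128 = 2.3% |
| 6 | 10 × 122/128 = 9.5% | 6/128 = 4.7% |

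**Effect on a comparison.** Take assumed true proportions of 10% (active) and 5% (placebo), with 3 never-dosed in each arm. The reported values are 10 × 125/128 = 9.77% and 5 × 125/128 = 4.88%.
- The risk ratio is 2.0 before and after, because the factor 125/128 cancels.
- The risk difference falls from 5.00 to 5 × 125/128 = 4.88 percentage points, a relative loss of 2.3%.

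**Effect on the primary analysis.** None. The 128 per arm, the 130 mL difference, the 350 mL standard deviation and the 80% power all concern trough FEV1 in ITT, and a separate safety set does not touch them.

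**The case against.** The case for leaving the text alone has four parts.

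1. *The group is nearly empty by design.* The Schedule of Activities bars randomization before eligibility is confirmed. The first double-blind dose is taken in clinic at Visit 2 (Section 5.1), and clinic dosing is supervised (Section 7.7). This stands, and it is why the point is minor.

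2. *Primary does not mean only.* The analysis plan could add a dosed set. That is true, but the main safety results would still rest on ITT as the protocol is written.

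3. *Details are deferred.* Section 10.6 says "Specific details for inclusion will be detailed in the RAP". That sentence follows one about data from participants who withdraw prematurely. It does not reopen the population definitions in 10.5.1, which are stated as a rule.

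4. *Ratios are unaffected.* With balanced non-dosing and no events among the never-dosed, this is correct. Only absolute proportions and differences move.

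A reader might also infer a stronger claim: that events after a wrong kit are credited to the wrong arm. The documents do not support it. Section 10.5.1 says who belongs to ITT. Nothing in the protocol says whether safety data are summarized by assigned or by received treatment, and that rule is commonly left to the analysis plan, which is not shown. Section 7.7 also provides a check at clinic dosing: "The dose of study treatment and study participant identification will be confirmed at the time of dosing".

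**Conclusion.** The point holds as a minor one. The protocol fixes a safety population that does not require exposure, and its exclusion of undosed participants omits those who receive a number at Visit 2 and never take a dose. On the assumed range of 0 to 6 per 128, adverse event proportions are understated by a relative 0% to 4.7%. This rests on an assumed k and on no events among the never-dosed. If non-dosing differed between arms, risk ratios would shift too, within the same bounds: at most a factor of 122/128 = 0.953 with 6 in one arm and none in the other.

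It would be wrong to argue from rare events that this flaw could double or erase an arm's count. At an assumed 1% incidence about 1% × 128 = 1.28 events are expected per arm, so any single event weighs heavily. But counting never-dosed participants moves no event between arms. Even with k = 6 it turns 1% into only 0.95% (1 × 122/128).

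**What to change.** Add to Section 10.5.1 a safety population: randomized participants who took at least one dose of double-blind treatment. Name it as the population for adverse events, events of special interest, ECG and vital signs. Limit the closing sentence of the ITT definition to efficacy, and leave the ITT definition itself unchanged.

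Do not close the gap by adding randomization failures to the randomized-in-error sentence. ITT is also the efficacy population, so that edit would remove randomized participants from the primary analysis because of something that happened after randomization.

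The cost is a short text change and one population flag. No new data are needed, because Section 7.7 already has the date and time of each clinic dose recorded in the eCRF. Sample size, power and the efficacy analyses do not change.

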10.5.2. Treatment Comparisons

To demonstrate the benefit of UMEC the primary comparisons of interest for the primary efficacy endpoint are:

- UMEC 62.5 mcg vs Placebo
- UMEC 31.25 mcg vs Placebo

Other pairwise treatment comparisons of interest that aim to informally estimate any potential benefit of increasing the UMEC dose are given below for all efficacy endpoints.

- UMEC 62.5 mcg vs UMEC 31.25 mcg

For the multiple comparisons and multiplicity adjustment, please see Section [10.5.3](#).

10.5.3. Multiple Comparisons and Multiplicity

In order to account for multiple tests involving the two UMEC doses a step-down testing procedure will be applied whereby inference for a test in the pre-defined hierarchy is dependent upon statistical significance having been achieved for the previous test in the hierarchy.

A step-down procedure with the following hierarchy will be used for the primary comparisons in the primary endpoint.

- The contrast between UMEC 62.5 mcg vs Placebo
(two-sided, alpha = 0.05. Null hypothesis of no treatment difference)
- The contrast between UMEC 31.25 mcg vs Placebo
(two-sided, alpha = 0.05. Null hypothesis of no treatment difference)

The second hypothesis will be formally tested only if the first hypothesis has been rejected, thus maintaining the overall significance level at 5%.

Specifically, if the defined treatment comparison for the primary efficacy endpoint at the highest dose of UMEC 62.5 mcg is significant at 0.05 level then the efficacy of UMEC 62.5 mcg is demonstrated, and the treatment comparison can be repeated on the UMEC 31.25 mcg dose.

Note that, in the event that the first hypothesis is not rejected a nominal p-value for the second hypothesis may be provided in the displays for descriptive purposes only and will not alter the conclusion of the step-down procedure.

No multiplicity adjustment will be made on these two treatment comparisons on the secondary endpoint.

For all efficacy endpoints (primary, secondary and other), treatment comparisons between UMEC 62.5 vs UMEC 31.25 mcg informally investigating the benefit of increasing UMEC dose will be made without adjusting for multiplicity. Any p-values ≤ 0.05 will be identified as nominally significant.

10.6. Statistical Analysis

Where possible, data from participants who withdraw prematurely from the study treatment or the study will be included in any relevant analyses. Specific details for inclusion will be detailed in the RAP.

In general, the baseline value is the last assessment value prior to randomization at Visit 2 for the efficacy endpoints based on assessments at clinic visits. The covariates to be considered in the efficacy analyses include age, sex, and the baseline value, if relevant. Other covariates, if appropriate, may be considered. Specific details will be provided in the RAP.

10.6.1. Primary Analyses

The primary efficacy endpoint is the mean change from baseline in trough FEV₁ at the end of the 24-week treatment period. For each participant, the baseline value of clinic FEV₁ is the last acceptable/borderline acceptable (pre-dose) FEV1 value obtained prior to randomization (either from Visit 2 pre-dose or from Visit 1 pre-bronchodilator).

The primary efficacy analysis will evaluate the “de facto” type estimand in the Intent-to-Treat population, using a mixed-model repeated measures (MMRM) analysis, including all trough FEV₁ recorded post randomization. Analyses will include the fixed, categorical effects of treatment, visit, treatment by visit interaction, sex, as well as the continuous, fixed covariates of age, baseline value, and baseline value by visit interaction. Point estimates and 95% confidence intervals will be calculated for the following primary comparisons of interest.

- UMEC 62.5 mcg vs Placebo
- UMEC 31.25 mcg vs Placebo

In addition, a de jure estimand, including data collected over the randomized double-blind treatment period, will be analyzed using a MMRM model. Sensitivity analyses to assess the impact of missing data will be detailed in the RAP.

Other pairwise treatment comparisons of interest as outlined in Section 10.5.2 will also be provided for the primary efficacy endpoint.

10.6.2. Secondary Analyses

Full details of the analyses to be performed on the secondary efficacy endpoint will be given in the RAP.

10.6.3. Other Analyses

Full details of the analyses to be performed on all efficacy endpoints, as well as details of time points to be analyzed, will be given in the RAP.

10.6.4. Interim Analyses

No interim analysis is planned for this study.

10.6.5. Exploratory Analyses

The psychometric properties of the E-RS and Supplemental asthma items will be evaluated to characterize the E-RS as an endpoint for asthma. These exploratory analyses may be provided in a separate RAP.

12. APPENDICES

12.1. Appendix 1: Abbreviations and Trademarks

Abbreviations

ACQ	Asthma Control Questionnaire
ADR	Adverse Drug Reaction
AE	Adverse Event
AESI	Adverse Event of Special Interest
ALT	Alanine Transaminase
AM	Morning
AQLQ	Asthma Quality of Life Questionnaire
AST	Aspartate Transaminase
ATS	American Thoracic Society
BMI	Body Mass Index
BPM	Beats Per Minute
BST	Bioanalytical Science and Toxicokinetics
BUN	Blood Urea Nitrogen
CI	Confidence Interval
CONSORT	Consolidated Standards of Reporting Trials
COPD	Chronic Obstructive Pulmonary Disease
DNA	Deoxyribonucleic acid
DPI	Dry Powder Inhaler
ECG	Electrocardiogram
(e)CRF	(Electronic) Case Report Form
eDiary	Electronic Diary
EOS	End of study
E-RS	Evaluating Respiratory Symptoms
ERS	European Respiratory Society
EW	Early Withdrawal
FDA	Food and Drug Administration
FEV1	Forced expiratory volume in 1 second
FF	Fluticasone Furoate
FP	Fluticasone Propionate
FSH	Follicle Stimulating Hormone
FVC	Forced Vital Capacity
GCP	Good clinical practice
GCSP	Global Clinical Safety and Pharmacovigilance
GINA	Global Initiative for Asthma
GSK	GlaxoSmithKline
hCG	Human Chorionic Gonadotropin
HIV	Human Immunodeficiency Virus
HPA	Hypothalamic Pituitary Axis
HRT	Hormone Replacement Therapy
IB	Investigator's Brochure

ICF	Informed Consent Form
ICH	International Conference on Harmonization
ICS	Inhaled Corticosteroids
IEC	Independent Ethics Committee
IOP	Intraocular Pressure
IP	Investigational Product
IRB	Institutional Review Board
IRT	Interactive Response Technology
IWRS	Interactive Web Response System
ITT	Intent to Treat
LABA	Long-Acting Beta-2-Agonists
LAMA	Long-Acting Muscarinic Antagonist
LOCS III	Lens Opacities Classification System III
LRTI	Lower Respiratory Tract Infection
MACE	Major Adverse Cardiac Event
MAOI	Monoamine Oxidase Inhibitors
MedDRA	Medicinal Dictionary for Regulatory Activities
mcg (μ g)	Microgram
MDI	Metered Dose Inhaler
mg	Milligram
min	Minute
mL	Milliliter
MMRM	Mixed-Model Repeated Measures
MSDS	Material Safety Data Sheet
msec	Millisecond
NIH	National Institutes of Health
NYHA	New York Heart Association
PEF	Peak Expiratory Flow
PK	Pharmacokinetic
PM	Evening
prn	As needed
QD	Once daily
QTc	QT interval corrected for heart rate
QTcB	QT interval corrected for heart rate by Bazett's formula
QTcF	QT interval corrected for heart rate by Fridericia's formula
RAP	Reporting and Analysis Plan
RBC	Red Blood Cell
RNA	Ribonucleic acid
SABA	Short-Acting Beta-2-Agonists
SAE	Serious Adverse Event
SGRQ	St. George's Respiratory Questionnaire
SPC	Summary of Product Characteristics
SRM	Study Reference Manual
TQT	Thorough QT
ULN	Upper Limit of Normal
UMECA	Umeclidinium

US	United States
VI	Vilanterol
VT	Ventricular Tachycardia
WBC	White Blood Cell

Trademark Information

Trademarks of the GlaxoSmithKline group of companies	Trademarks not owned by the GlaxoSmithKline group of companies
ELLIPTA	None

12.2. Appendix 2: Clinical Laboratory Tests

- All protocol required laboratory assessments (haematology, clinical chemistry and urinalysis) must be conducted in accordance with the Laboratory Manual, and Protocol Schedule of Activities (Section 2) Laboratory requisition forms must be completed and samples must be clearly labelled with the participant number, protocol number, site/centre number, and visit date. Details for the preparation and shipment of samples will be provided by the laboratory and are detailed in the Laboratory Manual. Reference for all safety parameters will be provided to the site by the laboratory responsible for the assessments.
- All blood samples which will be taken pre-dose, will be sent to a central laboratory for analysis (details provided in the Laboratory Manual). Standard reference ranges will be used.
- If additional non-protocol specified laboratory assessments are performed at the institution's local laboratory and result in a change in participant management or are considered clinically significant by the Investigator (e.g., SAE or AE or dose modification) the results must be recorded in the eCRF.
- Refer to the Laboratory Manual for appropriate processing and handling of samples to avoid duplicate and/or additional blood draws.
- Protocol-specific requirements for inclusion or exclusion of participants are detailed in Section 6 of the protocol.
- Additional tests may be performed at any time during the study as determined necessary by the investigator or required by local regulations.

Protocol-Required Safety Laboratory Assessments

Laboratory Assessments	Parameters							
Haematology	Platelet Count		RBC Indices:	WBC count with Differential:				
	Red Blood Cell (RBC) Count		MCV	Neutrophils				
	Hemoglobin		MCH	Lymphocytes				
	Hematocrit			Monocytes				
				Eosinophils				
				Basophils				
Clinical Chemistry¹	Blood Urea Nitrogen (BUN)	Potassium	AST (SGOT)	Total and direct bilirubin				
	Creatinine	Sodium	ALT (SGPT)	Total Protein				
	Glucose	Calcium	Alkaline phosphatase	Albumin				
Routine Urinalysis	
 Specific gravity pH, glucose, protein, blood and ketones by dipstick Microscopic examination (if blood or protein is abnormal) 							
Other Screening Tests	
 Follicle stimulating hormone (FSH) and estradiol (as needed in females of non-reproductive potential only) Serum/urine hCG Pregnancy test (as specified in the Schedule of Activities table [Section 2]) 							
NOTES:								

 1. Details of Liver Chemistry Stopping Criteria and Required Actions and Follow-Up Assessments after liver stopping or monitoring event are given in Section 8.1.1 and Appendix 7 								

